#### Secondary Objectives

- Assess usability of the system in clinical environments
- Determine impact of personalized difficulty adjustment on engagement and adherence
- Analyse accuracy and reliability of motion-tracking data
- Explore participant perceptions of motivation and user experience
- Identify barriers and facilitators to adopting gamified rehab technologies

## Planned Statistical Analyses

All analyses will be conducted **separately within each cohort** (Neurological and MSK), by original randomised allocation (intention-to-treat). Two-sided tests with  $\alpha = 0.05$  will be used throughout.

### 1. Descriptive / Feasibility Metrics

- **Recruitment rate:**
  - Number screened, number eligible, number randomised (%)
- **Retention & adherence:**
  - Proportion completing Week 8 assessment in each arm (%)
  - Mean ( $\pm SD$ ) number of sessions attended per arm
- **Data completeness:**
  - Proportion of missing outcome data at each timepoint

These will be reported as counts, percentages, and 95% confidence intervals.

### 2. Primary Outcomes

- **Neurological cohort:** Change in FMA-UE score (baseline → Week 8)
- **MSK cohort:** Change in SPADI score (baseline → Week 8)

#### Analysis:

- Analysis of covariance (ANCOVA) with Week 8 score as dependent variable, adjusting for:
  1. Baseline score
  2. Age
  3. Sex
  4. Randomisation stratum (high vs low severity)
- Report adjusted mean difference at Week 8 with 95% CI and p-value

### 3. Secondary Outcomes

1. **Functional independence:**
  - Neurological: Barthel Index change
  - MSK: DASH change
2. **Pain & ROM (MSK only):**
  - VAS pain change
  - Goniometric ROM change
3. **Usability & Engagement:**
  - SUS total score
  - Engagement survey score
4. **Motion-tracking metrics:**
  - Mean ROM achieved, movement smoothness, completion time, accuracy

#### Analysis:

- Continuous outcomes → ANCOVA as above.
- Repeated measures (baseline, Week 4, Week 8): mixed-effects linear models with fixed effects for time, arm, and timexarm interaction; random intercepts for participant.
- Categorical safety outcomes (adverse events): counts and  $\chi^2$  or Fisher's exact tests.

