## 5 STUDY DESIGN and METHODS of DATA COLLECTION AND DATA ANALYSIS

Type: Parallel, two-cohort (Neurological vs MSK), two-arm randomized controlled trial

- Arms (within each cohort):
  1. Usual-care physiotherapy only
  2. Combined ReHabGame + usual-care

Allocation: 1:1 randomisation, stratified by baseline severity (high vs low) within each cohort

- Blinding:
  - Outcome assessors blinded to group assignment

- Participants & therapists unblinded (interventions are overt)
- Duration: 6–8 weeks of intervention (2 sessions/week) + 4-week follow-up
- Sample size: 23 per arm per cohort (46 per cohort; 92 total), allowing ≈20% attrition.

Domain	Instrument & Timing
Demographics & History	Structured questionnaire at Week 0 (age, sex, diagnosis, time since onset/surgery, comorbidities)
Primary Outcomes	- Neurological: Fugl–Meyer Assessment (upper extremity) at Weeks 0, 8- MSK: SPADI at Weeks 0, 8
Secondary Outcomes	- Neurological: Barthel Index at Weeks 0, 8- MSK: DASH, pain VAS, goniometric ROM at Weeks 0, 8
Interim Metrics	At Week 4 for all: SUS, engagement survey, adverse-event checklist, quick FMA-UE subset (neuro) or SPADI re-test (MSK), Kinect snapshot metrics
Follow-up Metrics	At Week 12: SUS, engagement survey, adverse-event update, optional brief functional check
Motion-Tracking Data	Automatically logged each session via Kinect: range of motion, smoothness (jerk), repetition count, completion time, accuracy
Session Adherence	PDF session log (date, duration, pain VAS, issues) maintained by participant; automatically generated session report PDFs summarising movement metrics
Qualitative Feedback	Semi-structured interview or written feedback at end of Week 8 (usability, barriers, facilitators, motivation)
Safety Monitoring	Adverse events recorded at every session and via AE checklist at Weeks 4, 8, 12; severity and relatedness noted

All analyses conducted separately within each cohort on an intention-to-treat basis,  $\alpha = 0.05$  two-sided.

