### 2. Primary Analyses

- ANCOVA with Week-8 score as the dependent variable (adjusting for baseline value, age, sex, and severity stratum); report the adjusted mean difference (95% CI) between arms.

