### 3. Secondary & Repeated-Measures Analyses

- **Continuous outcomes** (Barthel, DASH, Pain VAS, ROM, SUS, engagement scores):
  - ANCOVA at Week 8 as above
  - **Mixed-effects linear models** for repeated measures (Weeks 0, 4, 8) with fixed effects for time, arm, and timexarm; random intercepts for participants
- **Categorical safety outcomes:** AE counts compared via  $\chi^2$  or Fisher's exact tests

4. **Motion-Tracking Metrics**
  - o Compare mean ROM, smoothness, completion time, and accuracy at Weeks 4 and 8 using ANCOVA, adjusting for baseline Kinect metrics
5. **Exploratory Analyses**
  - o **Cost/resource use:** descriptive comparison of therapist time and equipment costs per participant (t-tests or nonparametric equivalents)
  - o **Qualitative data:** thematic analysis of interviews to identify barriers/facilitators; representative quotes to illustrate key themes
6. **Missing Data**
  - o **< 5% missing:** complete-case analysis
  - o **≥ 5% missing:** multiple imputation by chained equations (20 datasets) including baseline covariates and outcomes
  - o **Sensitivity:** per-protocol analysis (≥ 75% sessions attended)
7. **Safety Review**
  - o AE rates summarised by arm; reviewed by an independent Data Monitoring Committee at midpoint (after ~50% complete)

All statistical programming and reporting will be done in R ( $\geq 4.0$ ), with scripts version-controlled for reproducibility.

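### The random-intercept model over Weeks 0, 4 and 8 can understate the Week 8 standard error where three visits exist, and most outcomes assigned to it lack three visits

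*Protocol*

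**What the plan says.** The model appears twice in the protocol. Under Planned Statistical Analyses, item 3 (Secondary Outcomes), it is "mixed-effects linear models with fixed effects for time, arm, and timexarm interaction; random intercepts for participant", for baseline, Week 4 and Week 8. Section 5, item 3, repeats it "for repeated measures (Weeks 0, 4, 8) with fixed effects for time, arm, and timexarm; random intercepts for participants". Neither statement lists baseline score, age, sex or severity stratum as covariates.

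The same continuous secondary outcomes also get an ANCOVA: "Continuous outcomes → ANCOVA as above" in the first place, and ANCOVA at Week 8 in the second. That ANCOVA is the primary model, "adjusting for baseline value, age, sex, and severity stratum". Neither analysis is named as the lead.

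Section 5 assigns the mixed model to "Barthel, DASH, Pain VAS, ROM, SUS, engagement scores". The section 5 data-collection table gives the measurement times:

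- "Neurological: Barthel Index at Weeks 0, 8", and DASH, pain VAS and goniometric ROM likewise at Weeks 0 and 8.
- SUS and the engagement survey first at Week 4. The Secondary Research Questions list them at Weeks 4, 8 and 12.
- At Week 4, a SPADI re-test (MSK), only a subset of the FMA-UE (neurological), and a Kinect snapshot.

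Allocation is 1:1, stratified by baseline severity within each cohort. All tests are two-sided at 0.05.

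**The concern.** With all three visits in the outcome vector and only a random intercept, the model gives every pair of visits the same correlation and every visit the same variance. It therefore applies one pooled within-person variance to every time contrast. Measurements eight weeks apart during treatment are plausibly less correlated than measurements four weeks apart. If so, the pooled figure is too small for the Week 0 to Week 8 contrast, which is the one of interest.

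Baseline also enters as an outcome with the arms free to differ at Week 0, so the contrast is a difference in change scores. That uses baseline less efficiently than ANCOVA does.

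At stake are the confidence intervals and p-values of a secondary analysis with about 18 completers per arm. The plan would also hold two Week 8 results for some outcomes, with nothing to say which one counts.

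**Working it through.** **Sample size used.** Section 7.2.1 expects at least 18 completers per arm and 72 in total from 23 randomised per arm with about 20% attrition. This reproduces: 23 × 0.8 = 18.4, so 18 per arm; 4 × 18 = 72. The protocol states no figure for the mixed model's error rate and no within-person correlation, so the correlations below are assumptions.

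**Three visits, closed form.** Take complete data and equal variances (SD = 1). Let D04, D48 and D08 be the within-person differences between Weeks 0-4, 4-8 and 0-8, with Var(D) = 2(1 − r). The model uses the mean of the three variances; the truth under simple allocation is Var(D08). So

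model SE / true SE = sqrt( mean[Var(D04), Var(D48), Var(D08)] / Var(D08) ),

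and the large-sample type I error is P(|Z| > 1.96 × ratio).

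| Assumed r (0-4 / 4-8 / 0-8) | Var(D04), Var(D48), Var(D08) | SE ratio | Type I error |
|---|---|---|---|
| 0.60 / 0.60 / 0.60 | 0.80, 0.80, 0.80 | 1.00 | 5% |
| 0.75 / 0.75 / 0.65 | 0.50, 0.50, 0.70 | sqrt(0.567/0.70) = 0.90 | 8% |
| 0.70 / 0.70 / 0.49 | 0.60, 0.60, 1.02 | sqrt(0.74/1.02) = 0.85 | 9.5% |
| 0.75 / 0.75 / 0.50 | 0.50, 0.50, 1.00 | sqrt(0.667/1.00) = 0.82 | 11% |
| 0.85 / 0.85 / 0.70 | 0.30, 0.30, 0.60 | sqrt(0.40/0.60) = 0.82 | 11% |

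**Simulation, simple allocation.** 20,000 null trials per scenario at 18 per arm gave 5.0%, 7.7% and 9.5% for the first three rows. ANCOVA stayed between 4.7% and 5.1% in every scenario of that run. For 0.70/0.70/0.49 the average model SE was 0.285 SD, the true SE 0.338 SD and the ANCOVA SE 0.294 SD.

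**Simulation, stratified allocation.** The trial stratifies by baseline severity. If that is represented by a median split on the baseline score (an assumption), part of the baseline imbalance disappears and the change contrast varies less. Rejection is then about 6% at 0.75/0.75/0.65, 8-9% in the last two rows, and about 4% with equal correlations.

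**Two visits (Barthel, DASH, VAS, ROM).** There is only one correlation, so the SE is valid: simulated type I error was 4.6-5.3%. The cost is precision. Under simple allocation the change score has variance proportional to 2(1 − r) and ANCOVA to 1 − r², so the SE ratio is sqrt(2/(1 + r)):

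- r = 0.8: sqrt(2/1.8) = 1.05
- r = 0.4: sqrt(2/1.4) = 1.20

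Stratifying on baseline narrows this gap.

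**No baseline (SUS, engagement).** A model over Weeks 0, 4 and 8 has no Week 0 data to use.

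**Role of the stratum.** One simulated data set was fitted with and without a stratum main effect. The Week 8 time-by-arm estimate was −0.2099 with SE 0.2424 both times. A person-level main effect cancels from a within-person contrast.

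**Agreement with ANCOVA.** Under no effect, both estimators averaged within 0.004 SD of zero and correlated 0.85-0.95. Within one trial they differed with an SD of 0.06-0.18 outcome SD.

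**The case against.** The strongest reply is that the damaging case is rare here. Of the clinical scores, only SPADI is fully repeated at Week 4. SPADI is a primary outcome analysed by ANCOVA, and section 5 does not list it for the mixed model. The Week 4 FMA-UE is a subset, and section 5 gives the Kinect metrics their own ANCOVA. This largely stands, and it limits the point. It does not remove it: the first statement of the model names no outcomes, its section includes the motion-tracking metrics, and the schedule in Appendix 2 marks functional assessment at Weeks 0, 4 and 8 without naming instruments.

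A second reply is that the size depends on assumed correlations, that equal correlations give no inflation, and that stratified allocation lowers the figures. All of that stands and is why ranges are given.

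A third is that covariance structure is normally left to an SAP. Here, though, the protocol itself fixes the random-intercept form twice.

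A reader might also infer that leaving out the randomisation stratum causes the wrong standard error. It does not, because a stratum main effect cancels from this contrast. Nor do the documents support saying that the two analyses must disagree. They target the same arm effect and differ only through chance baseline imbalance and precision.

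**Conclusion.** The point holds in a limited form, and its severity is minor.

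- **Same instrument at Weeks 0, 4 and 8** (clearly SPADI; possibly FMA-UE subset items or Kinect metrics): if correlation weakens over time, the Week 8 standard error is too small. Type I error is about 6-9% with stratified allocation and 8-11% with simple allocation, against about 5% for ANCOVA.
- **Weeks 0 and 8 only** (Barthel, DASH, VAS, ROM): the inference is valid but less precise than the ANCOVA already planned, by at most about 5-20% for correlations of 0.8-0.4.
- **No Week 0 value** (SUS, engagement): the model as written cannot be fitted.

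These sizes assume complete data, about 18 completers per arm, equal variances and the stated correlations; the stratified figures also assume a median split on baseline. The primary analysis is not touched, and the protocol says that the pilot is not sized for confirmatory testing.

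**What to change.** Change both statements of the model (Planned Statistical Analyses, item 3, and section 5, item 3):

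1. Limit the repeated-measures model to outcomes with the same instrument at Weeks 0, 4 and 8, and name them.
2. For those, use Weeks 4 and 8 as outcomes, with baseline score, age, sex and severity stratum as covariates; visit, arm and visit-by-arm; an unstructured covariance; REML; and small-sample degrees of freedom. The stratum belongs here to match the ANCOVA, not to repair the standard error.
3. Use ANCOVA alone for outcomes at Weeks 0 and 8 only, and name it as the lead Week 8 analysis.
4. Take SUS and engagement off the list for the Weeks 0, 4, 8 model and state separately how they are compared, since they have no baseline.

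The cost is some wording, a small change of R code, and a few extra covariance and covariate parameters to estimate. No new data are needed.

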#### 4. Exploratory & Cost Analyses

- **Cost/resource use:** Therapist time and equipment cost per participant—summarised descriptively and compared by arm (t-tests or nonparametric equivalents).
- **Qualitative feedback:** Thematic analysis of interview transcripts to identify barriers and facilitators; illustrative quotes reported.

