## Exploratory Aims

1. Compare **cost and resource utilization** (therapist time, equipment) across arms.
2. Identify **barriers and facilitators** to adoption of gamified rehabilitation via participant interviews.
3. Assess **safety outcomes** (adverse events, overuse symptoms) and determine whether combined therapy introduces any incremental risk.

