## 4.2 Outcome

**Broad Outcome:** A clearer understanding of how a markerless, game-based rehabilitation system affects upper-limb motor recovery, motivation, and overall functional independence.

**Practical Impact:** Evidence to support (or refute) the use of ReHabGame as a routine therapeutic tool, potentially informing clinical guidelines and future technology-driven rehabilitation strategies.

After each gamified rehabilitation session, participants will receive personalised, visual performance feedback generated by the ReHabGame platform. This includes:

- A PDF-based summary showing:
  - Percentage of movement types (e.g. abduction, adduction of the upper arm)
  - Distribution of virtual objects around the participant in the game environment
  - Visual markers of target reach, joint usage, and task completion
- Feedback is presented immediately post-session in a simple, colour-coded format that participants can understand without technical expertise.

A member of the research team will review this feedback in person with the participant to:

- Celebrate progress and encourage engagement
- Clarify what the data means in lay terms
- Address any confusion or concern
- Adjust future gameplay settings if needed to support optimal challenge and safety

The ReHabGame system uses an **automated, performance-based algorithm** to dynamically adjust the difficulty level of gameplay in real time. This ensures that exercises remain **appropriately challenging, engaging, and within the user's capabilities**, thereby reducing frustration and promoting sustained participation.

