**Site A: Southend General Hospital (NHS)**

**Cohort:** MSK only.

**Recruitment:** Patients with eligible musculoskeletal shoulder conditions will be identified from outpatient orthopaedic and physiotherapy clinics.

All interventions will be delivered on-site by NHS physiotherapists trained in the study protocol.

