## Staff Training

- Staff at both sites will receive a brief orientation on ReHabGame's operation, the motion-tracking sensors, and participant safety protocols.
- Any site-specific health and safety training required by hospital policy (e.g., manual handling, infection control) must be completed by the research team.

1. Identification & Recruitment
  - At each site, clinical teams (physiotherapists, occupational therapists, rehab consultants) will introduce the study to eligible patients and, if they express interest, refer them to the research team for formal screening.
  - Potential participants will receive an information sheet and have an opportunity to ask questions before providing written informed consent.
2. Baseline Assessments
  - Participants will undergo baseline clinical evaluations (e.g., Fugl-Meyer Assessment), and relevant questionnaires.
  - These may take place in a private clinic room or dedicated rehabilitation space.
3. ReHabGame Intervention
  - Participants will use ReHabGame in designated therapy areas equipped with the Kinect hardware.
  - Session frequency and duration will follow the study protocol (e.g., 1–2 sessions per week over 6–8 weeks).
  - Research staff or designated clinical staff will supervise sessions, ensuring correct usage and participant safety.
4. Data Collection
  - Quantitative: System logs (range of motion, frequency of play), standardized clinical scales (pre-/post-intervention).
  - Qualitative: Questionnaire to gather feedback on user experience and feasibility.
5. Follow-Up Assessments
  - Post-intervention evaluations will be conducted to assess changes in upper-limb function and gather final feedback.
  - Data will be entered into secure, password-protected electronic databases, ensuring confidentiality and compliance with data protection laws.

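### The exploratory cost comparison counts only therapist time and equipment, so research-team time used only in the combined arm can go uncounted

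*Protocol*

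**What the plan says.** The resource comparison appears four times in the Protocol, each time with the same two components, therapist time and equipment: in the Study Summary (exploratory objectives), in Planned Statistical Analyses under Exploratory & Cost Analyses ("Therapist time and equipment cost per participant—summarised descriptively and compared by arm"), in the Exploratory Aims of section 4.1, and in the Exploratory Analyses item of section 5.

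On who works with combined-arm participants during and after a game session, the Protocol says:

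- Section 6, Staff Training, item 3: "Research staff or designated clinical staff will supervise sessions, ensuring correct usage and participant safety".
- Section 4.2, on the performance feedback issued after each game session: "A member of the research team will review this feedback in person with the participant". The same person may adjust later game settings.
- Section 6, Site A (the whole MSK cohort): "All interventions will be delivered on-site by NHS physiotherapists trained in the study protocol".
- Section 6, Site Readiness (Site B, the whole neurological cohort): intervention sessions run under the direct supervision of the site's lead physiotherapist.

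On data capture, the section 5 table lists a "PDF session log (date, duration, pain VAS, issues) maintained by participant", together with automatic movement reports. Section 7.3.2 allows an optional QR scan that logs time and session type. Neither that table nor the Appendix 2 schedule has an item for staff role or staff minutes.

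**The concern.** The trial compares usual care with usual care plus supervised game sessions. The resource question is what the added component consumes. Both arms are scheduled for the same therapist-led physiotherapy, so the difference between arms lies in the equipment, the staffing of the game sessions and the feedback review. The chosen measure picks up the equipment. It picks up the staffing only when a therapist provides it.

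The feedback review is assigned to the research team, and supervision may be. Both occur only in the combined arm, so whatever is left out makes that arm look less resource-intensive. The background and rationale present limited therapist time and resource-heavy care as part of the problem, so this is the direction in which an error would mislead. A second risk is comparability: if physiotherapists run the game at one site and research staff at the other, the same variable includes game supervision in one cohort and excludes it in the other.

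**Working it through.** The Protocol gives no cost or staff-time figure to reproduce. The check is arithmetic on scheduled contact time.

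**Inputs**
- Game sessions: 2 per week for 6 to 8 weeks, 30 to 45 minutes each (Study Timeline and Procedures, Intervention Sessions; Study Summary).
- Usual care: the same frequency, duration and session length, in both arms (same section).
- Combined arm: 23 participants per cohort (sections 5 and 7.2.1).
- Length of the feedback review: not stated. I assume 5 to 15 minutes to show a range.

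**Scheduled time per participant**
- Game sessions: 2 × 6 = 12 to 2 × 8 = 16.
- Game contact: 12 × 30 = 360 min (6 h) to 16 × 45 = 720 min (12 h).
- Usual care in either arm: also 6 to 12 h.
- Combined arm before feedback: 12 to 24 h, so the ratio to usual care is 2.0.
- Feedback review (assumed length): 12 × 5 = 60 min to 16 × 15 = 240 min, i.e. 1 to 4 h.
- Ratio including feedback: from (2 × 16 × 45 + 16 × 5) / (16 × 45) = 2.1 to (2 × 12 × 30 + 12 × 15) / (12 × 30) = 2.5.

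**What therapist time alone would record**
- *Site A, MSK.* Physiotherapists deliver all interventions, so game sessions count and the recorded ratio is about 2.0. The feedback review is missed: 1 to 4 h per participant on the assumed length.
- *Site B, neurological, if therapists supervise.* Same as Site A.
- *Site B, if research staff supervise every game session.* The recorded ratio is 1.0. The missed supervision is 6 to 12 h per participant, or 23 × 6 = 138 h to 23 × 12 = 276 h at full attendance, with the feedback review on top.

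**Sensitivity**
- At the 18 completers per arm that section 7.2.1 expects as a minimum, the Site B figure is 18 × 6 = 108 h to 18 × 12 = 216 h.
- Staff Training item 3 gives 1 to 2 game sessions per week, which does not match the 2 per week stated elsewhere. At one per week for 6 weeks the lower end is 6 × 30 = 180 min, or 3 h per participant. These passages also need reconciling.

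**Could the logs recover it?** Duration, and optionally time and session type, would allow contact time to be derived by modality. They would not show whose time it was or how long the feedback review took.

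**The case against.** The strongest reply is that the site descriptions largely answer the point. At Site A, physiotherapists deliver everything, so game supervision there is therapist time. At Site B, sessions are under a physiotherapist's direct supervision and the clinic delivers the intervention. The sentence allowing research staff is generic and equally allows clinical staff. Therapist time is also the scarce resource named in the background, so measuring it answers a legitimate question. Finally, the outcome is exploratory and descriptive, in a pilot that says it is not powered for definitive testing, and costing detail often sits in other documents.

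Much of this stands, and it rules out two stronger readings that a reader might infer. One is that the combined arm's extra staff time will be recorded as zero across the trial, with 46 × 6 = 276 to 46 × 12 = 552 hours lost. The Site A text contradicts that for half of those participants, and the Site B text makes it only a possible extreme for the rest. The other is that nothing relevant is collected. Session duration is logged, and equipment prices and unit costs need no visit and can be set elsewhere.

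What the reply does not remove is the feedback review, which is assigned to the research team at both sites and falls outside the measure. Nor does direct supervision by one lead clinician say who is in the room for each session, or whose minutes are counted. An analysis plan can redefine a variable, but it cannot recover role and minutes that were never recorded.

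**Conclusion.** The point holds in limited form. As written, the comparison leaves out research-team time that occurs only in the combined arm, so it can understate that arm's resource use and cannot overstate it by this route. For the MSK cohort the omission is mainly the feedback review, whose size depends on a length that the Protocol does not give. For the neurological cohort the omission of supervision time lies between nothing and 6 to 12 h per participant (138 to 276 h in total). The upper end assumes research staff at every game session, 2 sessions per week and full attendance. The variable may also differ in content between the cohorts.

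The Practical Impact statement in section 4.2 might be read as offering the cost result as evidence for routine use. It does not mention cost; it follows a statement about recovery, motivation and independence. The consequence is confined to an exploratory outcome, and the primary, secondary and safety analyses are untouched. The change is still worth making before recruitment, because the missing information cannot be reliably reconstructed later.

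**What to change.** 1. In the Study Summary, Exploratory & Cost Analyses, the Exploratory Aims and the section 5 Exploratory Analyses item, replace therapist time with *staff time by role (therapist, other clinical, research staff)*. State that it covers game supervision, set-up and feedback review. Report therapist time separately within it, so the question about therapist capacity is still answered.
2. Add one staff-completed line to the session record in both arms: role, minutes, modality. List it in the section 5 data-collection table and in Appendix 2.
3. Reconcile the Site A, Site Readiness and Staff Training passages on who staffs game sessions.

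The cost is about a minute of entry per session and, probably, a less favourable resource figure for the combined arm. Unit costs and equipment prices can stay in other study documents.

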### 3. Intervention Sessions (Weeks 1–8): Questionnaire at week 2, 4, 8 (**via the above Link**)

- Combined arm only; 2x/week, Weeks 1–8

Usual care only:

- o 30–45 min therapist-led physiotherapy per session
- o 2 sessions/week for 6–8 weeks (standardised protocol)
- **Combined care- Usual-care + ReHabGame:**
  - o 30–45 min Kinect-guided exercises per session.
  - o Real-time difficulty adaptation; metrics auto-logged.
  - o Both modalities, each 2x/week (on separate days or back-to-back).
  - o Each session is logged in the PDF format.

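### The planned tests of therapist time and equipment cost compare quantities that differ between arms by schedule; the increment with a confidence interval would be more useful

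*Protocol*

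**What the plan says.** Two places fix the cost analysis. Planned Statistical Analyses, item 4 (Exploratory & Cost Analyses), has therapist time and equipment cost per participant "summarised descriptively and compared by arm (t-tests or nonparametric equivalents". Section 5, in the list of analyses under Exploratory Analyses, gives a "descriptive comparison of therapist time and equipment costs per participant (t-tests or nonparametric equivalents". The opening of Planned Statistical Analyses applies a two-sided 5% level to all tests, within each cohort. The aim served is the exploratory one in Section 4.1, comparing cost and resource use ("therapist time, equipment) across arms").

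The schedule is under Study Timeline and Procedures, item 3 (Intervention Sessions). Usual care is "30–45 min therapist-led physiotherapy per session", at "2 sessions/week for 6–8 weeks (standardised protocol". The combined arm adds Kinect-guided sessions of 30–45 min: "Both modalities, each 2x/week (on separate days or back-to-back".

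On who delivers the sessions, Section 6 says of Site A (MSK): "All interventions will be delivered on-site by NHS physiotherapists trained in the study protocol". The ReHabGame Intervention item under Staff Training, also in Section 6, instead allows either research staff or designated clinical staff to supervise game sessions, and gives a frequency of 1–2 per week. Site Readiness places the neurological site's sessions under its clinical lead's supervision and mentions a dedicated computer and Kinect sensor.

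**The concern.** A two-sample test asks whether the arms could share the same distribution or mean. Here the protocol's own schedule largely settles that before any data arrive. The combined arm is assigned extra sessions and extra equipment, so a difference in game-equipment cost, and in therapist time where therapists run those sessions, follows from allocation and says nothing about what ReHabGame does to resource use.

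Two quantities would help in planning a later trial: how large the increment per participant is, and whether therapist time in usual-care sessions changes when the game is added. A test on total therapist time merges the second into the scheduled increment. A rank test, which the plan also allows, does not estimate a difference in mean minutes or mean cost. A reader of the final report could take a very small p-value as a finding about the system when it only restates the design.

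**Working it through.** **Inputs from the protocol.** Usual care: 2 sessions/week, 6–8 weeks, 30–45 min. Combined arm: usual care plus game sessions of 30–45 min, each modality 2/week. Sample (Section 7.2.1): 23 per arm per cohort, at least 18 completers. Two-sided 5% level.

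**The plan's own figure.** 18 / (1 − 0.20) = 22.5, rounded up to 23; and 23 × 0.80 = 18.4. The stated 23 and 18 agree with 20% attrition.

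**Scheduled contact time** (sessions/week × weeks × minutes):

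| Weeks | Min/session | Usual care | Combined | Ratio |
|---|---|---|---|---|
| 6 | 30 | 2×6×30 = 360 | 4×6×30 = 720 | 2.0 |
| 6 | 45 | 540 | 1080 | 2.0 |
| 8 | 30 | 480 | 960 | 2.0 |
| 8 | 45 | 720 | 1440 | 2.0 |

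Contact time doubles at every combination. How much of the added half is therapist time is not defined.

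**Therapist-time test.** Let f be the added therapist time as a fraction of mean usual-care time, and CV the standard deviation divided by that mean. The protocol gives no variance, so CV is assumed at 0.2 to 0.5, equal in both arms, with usual-care time unchanged. The noncentrality is f / (CV × √(2/n)) on 2n − 2 degrees of freedom. Example: f = 0.5, CV = 0.5, n = 18 gives 1 / √(2/18) = 3.0 and rejection probability 0.83. Over n = 18 to 23 and CV 0.2 to 0.5:

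| Therapist time counted per game session | f | Rejection probability |
|---|---|---|
| All | 1 | >99.9% |
| Half (or one therapist-run game session/week) | 0.5 | 83–100% |
| A quarter | 0.25 | 31–99% |
| None | 0 | 5% |

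**Simulation check** (1,500 trials per setting; 6–8 weeks, 30–45 min, 80% mean attendance varying between participants, all assumed; t-test and Mann-Whitney; 18 and 23 per arm):

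- All counted: 100%.
- Half counted: 98.6–99.7%.
- A quarter counted: 62–77%.
- None counted: 4.6–5.4%.
- All counted, usual-care time cut by 25%: still 100%. The saving is invisible in the p-value.
- Half counted, usual-care time halved: 4–6%. A large change in usual care is cancelled by the scheduled increment.

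**Equipment test.** Take game-equipment cost as zero in usual care and positive in the combined arm, 18 per arm. With the same cost for every combined participant, Mann-Whitney gives p = 3.7 × 10⁻⁹, and the t-test has no within-arm variance. With one simulated set of costs that vary between participants, the t-test gives 2.8 × 10⁻⁹ and Mann-Whitney 4.7 × 10⁻⁸. The rank result does not depend on the unit cost, because the arms separate completely.

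**The case against.** A reader might infer that the therapist-time test must be significant whatever ReHabGame does. The documents do not support that. The physiotherapist-delivery statement covers Site A only. The Staff Training text permits research staff to supervise, and the Difficulty Adjustment Logic in Section 4.2 says the game adapts without a therapist's input. If that supervision is not counted, rejection is about 5% when usual-care time is unchanged, so the test can respond to therapist involvement. This objection stands and limits the point for therapist time.

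A reader might also infer that the plan would leave the size of the increment unreported. That goes too far: both places promise a descriptive comparison, so arm means will be visible, and standard t-test output includes an interval for the difference. Still, neither place commits to reporting that interval or to separating time by session type, and the rank option does not estimate a mean difference.

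Equipment costing is not defined. If usual-care equipment were also costed, the control arm would not be zero. The argument therefore concerns game equipment.

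Nor is usual-care time the only component that could change: supervision of game sessions can vary too. Finally, this is an exploratory aim in a pilot that Section 7.2.1 says lacks power for definitive testing. That is why the point is minor. It also favours estimation over testing.

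**Conclusion.** The point holds in limited form. The p-value for game-equipment cost is uninformative because only one arm uses that equipment. The p-value for therapist time mainly reflects the delivery schedule and an unstated counting rule. Rejection runs from about 5% when no game-session supervision is counted to about 100% when every game session is therapist-run, with usual-care time unchanged. Where physiotherapists deliver all sessions, as stated for the MSK site, the test rejects even if usual-care time falls by a quarter.

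These figures rest on assumed variances (CV 0.2 to 0.5), assumed attendance of 80%, and 18 to 23 participants per arm. They do not show that the test can never discriminate. No primary outcome or sample size depends on it. This is a worthwhile improvement, not an error that threatens the trial.

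**What to change.** In Planned Statistical Analyses, item 4, and under Exploratory Analyses in Section 5:

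1. Replace the t-tests and nonparametric tests with the between-arm difference in arithmetic mean therapist minutes and mean cost per participant, with a 95% CI (for example bootstrap), by cohort.
2. Report therapist time in usual-care sessions separately from therapist time in game sessions.
3. State whether supervision of game sessions counts as therapist time.
4. Present game equipment as a unit cost, not as a tested outcome.

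In addition, reconcile the Site A and Staff Training text on who supervises game sessions, and the Intervention Sessions and Staff Training text on how often they occur. The scheduled increment depends on both.

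Cost: rewording of two short paragraphs, a few lines of R, and no p-value for cost. Session type and therapist minutes must be logged routinely. The QR scan in Section 7.3.2 can record time and session type, but it is optional, and neither it nor the Section 5 session log specifies therapist minutes.
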